#### Standard scales:

- Positive and Negative Affect Scale (PANAS; Watson et al., 1988)
- Rosenberg Self Esteem Scale (Rosenberg, 1965)
- Profile of Mood States (POMS) Scale (McNair et al., 1971)
- Altman Self-Rating Mania Scale (Altman et al., 1997)
- Quick Inventory of Depressive Symptomatology (QIDS-SR 16; Rush et al., 2003)
- Brief Implicit Association Test (BIAT; Greenwald et al., 1998)
- Dysfunctional Attitudes Scale (Weissman & Beck, 1978)
- Childhood Trauma Questionnaire (CTQ; Bernstein & Fink, 1998)
- Hypomania Check List (Angst et al., 2005)

Standard neuropsychological tests:

 Standard neuropsychological tests of language, emotional and social cognition, memory, praxis and attention in patients with suspicion of cognitive impairments (Addenbrooke's Cognitive Examination-III; Hsieh et al., 2013)

Experimental neuropsychological tests/scales:

- Short version of the value-related moral sentiment task
- Additional ratings of autobiographical memories associated with self-blame and otherblame
- Causal social agency inference and evaluation task

## 5. Inclusion/Exclusion Criteria

All participants are screened over the phone for inclusion and exclusion criteria after being informed and asked for oral consent before formal evaluation.

Psychiatric diagnoses after the screening are established using an unstructured clinical interview by a psychiatrist and via a structured interview using the Structured Clinical Interview (SCID-I) for the Diagnostic and Statistical Manual of Mental Disorders (DSM). The clinical evaluation also includes a physical examination & history taking and a brief psychiatric family history screening questionnaire. Participants can take part in all studies if they fulfil the inclusion and exclusion criteria. Informed consent is obtained separately for each study and session to monitor continued consent.

### 5.1. Inclusion criteria

Participants meeting the following criteria will be considered for inclusion into the studies: MDD Patients

- Recurrent major depressive disorder (MDD) according to DSM-V with at least one major depressive episode (MDE) of at least 2 months duration, insufficiently remitted for at least 6 weeks, so that they display symptoms that are significantly bothering or impairing (Psychiatric Status Rating of 3-5 over the past 2 weeks on Longitudinal Interval Follow-up Interview (Keller et al., 1987)
- If treated with antidepressants, on stable dose for at least 6 weeks prior participation and planning to stay on this dose for the duration of the study
- Patients have insufficiently responded to at least one course of cognitive behavioural therapy (CBT) or antidepressants or are not amenable to these standard treatments and are not currently undergoing psychotherapy.
- Age range: 18 or older
- Right-handedness in order to ensure homogenous response to our right hemisphere treatment target.
- Proficieny in English in order to ensure reliable responses on newly developed secondary outcome measures

#### Control Groups:

- Age-matched and education matched to respective study population
- Proficient in English
- Right-handedness
- Panic Disorder patients: Diagnosis obtained according to the DSM; insufficient remission of symptoms for at least 6 weeks, no other relevant psychiatric or neurological disorders in history or currently
- Healthy volunteers: No psychiatric or neurological disorders in history or currently

#### 5.2. Exclusion criteria

A participant will not be eligible for inclusion if any of the following criteria applies:

- Standard MRI contraindications such as exclusion of participants with any kind of non-removable ferromagnetic devices or implants due to possible dangerous effects of the MRI magnet upon metal objects in the body
- History of learning disabilities or developmental disorders
- Impairments of vision or hearing which cannot be corrected during the experiment
- History of manic or hypomanic episodes, of schizophreniform symptoms or schizophrenia, of substance abuse, neurological disorders such as seizures, loss of consciousness following brain injury or medical disorders affecting brain function, blood flow or metabolism
- Current intake of benzodiazepines, GABAergic or benzodiazepine receptor agonists
- Current recreational drug use
- Pregnancy

#### MDD Patients

- Greater than low risk of suicidality or violence
- Current MDE with a duration of more than one year
- Prior specialist diagnosis of ADHD, antisocial or borderline personality disorder
- Significant impairment of psychosocial functioning (at least moderate impairment in interpersonal, work or leisure domains on the Longitudinal Interval Follow-up Interview [LIFE]) in the year prior to the last MDE as a sign of a possible co-morbid personality disorder

Current self-harming behaviours

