#### 2.2.1. Specific aim and hypothesis

Case-control study to investigate neurocognitive mechanisms underpinning self-blame bias in major depressive disorder compared with panic disorder and healthy control participants. This study will gather the first evidence how specific self-blaming biases previously demonstrated in MDD (Green et al., 2013) are when compared with another mental health disorder. Further, a novel experimental task will be applied investigating whether changes in social agency inferences underpin self-blaming biases in MDD. We hypothesise that patients with MDD show self-blaming emotional biases and overgeneralisation of self-agency for failure when compared with panic disorder and healthy control participants. In case participants perceive the implied neurocognitive testing as emotionally distressing, they are offered consultation by a psychiatrist.

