#### Control Groups:

- Panic Disorder patients: history of MDD or other relevant psychiatric or neurological disorders
- Healthy volunteers: history of axis-I disorder in family; history of psychiatric disorders or psychotropic medications

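### Study 2 excludes MDD patients for suicide or violence risk and current self-harm but sets no matching rule for panic patients, so its two patient groups pass different risk filters

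*Protocol*

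**What the plan says.** Protocol 2.2.1 gives the purpose of Study 2 as specificity: "This study will gather the first evidence how specific self-blaming biases previously demonstrated in MDD" are when MDD is compared with another disorder. The hypothesis is that MDD patients show more self-blaming bias than panic and healthy participants.

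Section 5 does not split the MDD criteria by study, and Protocol 2.2.2 lets Study 2 take MDD data from Study 1. The MDD exclusions therefore govern the Study 2 case group. Under the MDD Patients heading of 5.2 they are:

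- "Greater than low risk of suicidality or violence"
- "Current self-harming behaviours"
- "Prior specialist diagnosis of ADHD, antisocial or borderline personality disorder"
- at least moderate impairment of functioning on the LIFE interview "in the year prior to the last MDE as a sign of a possible co-morbid personality disorder"
- a current episode lasting more than one year.

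For panic patients, 5.1 (Control Groups) requires "insufficient remission of symptoms for at least 6 weeks, no other relevant psychiatric or neurological disorders in history or currently", and 5.2 (Control Groups) excludes a "history of MDD or other relevant psychiatric or neurological disorders".

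**The concern.** A specificity contrast between two disorders is easiest to read when the groups differ in diagnosis and are otherwise selected alike. The protocol accepts this aim. Protocol 2.2.2 permits antidepressants in panic patients so that they are comparable with the MDD group, and 5.1 matches controls on age and education. Suicide or violence risk and self-harm are not aligned in the same way.

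Panic is the only patient comparator in Study 2. If self-blame is higher in people who self-harm or are at raised suicide risk, removing them from the MDD group alone lowers that group's mean relative to panic. A small or null difference could then be read as showing that self-blame is not specific to MDD, when part of it came from selection.

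**Working it through.** The plan gives no Study 2 figure to reproduce: no effect size, significance level or power. The check is a comparison of the criteria.

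| Feature | MDD (5.2) | All groups (5.2) | Panic (5.1, 5.2) | Reading |
|---|---|---|---|---|
| Suicide or violence risk above low | Excluded | Not mentioned | Not mentioned | Mismatch |
| Current self-harm | Excluded | Not mentioned | Not mentioned | Mismatch |
| Antisocial or borderline personality disorder | Excluded if diagnosed by a specialist | Not mentioned | May fall under other relevant psychiatric disorders | Unclear wording |
| ADHD | Excluded if diagnosed by a specialist | Developmental disorders excluded | May also fall under other relevant disorders | Unclear wording |
| Poor functioning before the last MDE | Excluded | Not mentioned | Not mentioned; no MDE to anchor it | Mismatch that cannot be copied across literally |
| Current MDE over one year | Excluded | Not applicable | Not applicable | Specific to depression |

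**Does the general panic exclusion close the first two rows?** It does not, for two reasons. Suicide risk, violence risk and self-harm are states or behaviours, and the panic wording speaks of disorders. Also, the Study 1 synopsis already excludes MDD patients with other current or relevant past axis-I disorders and lists suicide and violence risk as a separate item. The sponsor thus did not treat a comorbidity filter as covering risk.

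**Which way would the mismatch push?** Write D for the MDD-minus-panic difference in self-blame, in SD units, that would be seen if both groups were selected alike. Then

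observed difference = D − s_M + s_P + b

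- s_M is the fall in the MDD mean caused by the MDD-only exclusions.
- s_P is the fall in the panic mean caused by requiring no MDD history and no other relevant psychiatric disorder.
- b is the net effect of the Psychiatric Status Rating band of 3 to 5, which 5.1 applies to MDD only. The band has a floor as well as a ceiling, so b can take either sign.

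Under a truncated-normal model, a filter that removes the top fraction q on a trait correlated r with self-blame lowers the mean by r × φ(z)/(1 − q), where φ is the standard normal density and z is its 1 − q quantile. With r above zero s_M is positive, and taken alone it shrinks the contrast. If the panic filters act with the same q and r, then s_P = s_M and the two cancel. The documents give neither q nor r for either group and nothing that fixes b. The sign of s_M follows from the assumption about r; the sign and size of the total do not follow from anything in the protocol.

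**The case against.** The best case against the point is that the panic group is itself filtered. It must be free of MDD, past or present, and of other relevant psychiatric disorders, and the all-group list removes substance abuse, mania, schizophrenia and benzodiazepine use. Requiring no MDD history may well remove many panic patients with high self-blame or self-harm. This stands, and it is why the net direction is left open. A reader might infer that the panic comparator is unselected, or that personality disorder is allowed in it. The text supports neither: a diagnosed personality disorder can fall under the panic exclusion, and the fault there is that *relevant* is undefined.

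The functioning criterion is offered as a marker of possible comorbid personality disorder and is tied to an MDE. It is not a cut on current severity, and it cannot simply be moved to panic patients. This also stands.

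A reader might want to state a loss of power, or to ask for the Psychiatric Status Rating band in panic patients. Any power figure would rest wholly on an assumed effect, assumed removal fractions and no filtering of panic patients, and the last of these conflicts with 5.1 and 5.2. The band has a floor that raises the MDD mean, so it is not evidence of one-sided trimming.

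It can also be said that Section 4 gives every group baseline BDI-II, MADRS and QIDS scores, so severity can be adjusted for. This does not replace aligned selection. Depression scores are part of what defines the cases, so adjusting for them removes part of the contrast under study, and they are not measures of violence risk or self-harm.

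MDD patients may come from a treatment trial, which is a plausible reason for stricter risk rules, but the protocol does not give it. Nor should the mismatch be read as a safety defect: Study 2 is observational, and 2.2.1 offers a psychiatric consultation to anyone distressed by the testing.

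**Conclusion.** The point holds in a limited form. For suicide or violence risk and for current self-harm, the MDD and panic groups in Study 2 are selected by different rules unrelated to diagnosis, and the protocol does not justify the difference. That much follows from the text alone. Attenuation of the MDD-panic contrast is a possibility. It depends on these features going with self-blame and on the panic filters not offsetting the loss, and the documents settle neither. For ADHD and personality disorder the defect is unclear wording; for prior functioning it is a criterion with no panic equivalent. The point concerns only the observational comparison in Study 2. It is worth correcting because the change is cheap and the contrast affected is the one that carries the specificity claim.

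**What to change.** In Protocol 5.2:

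1. Move the suicide or violence risk exclusion and the current self-harm exclusion from the MDD list to a heading that covers both patient groups. If the difference is intended, state the reason.
2. State whether other relevant psychiatric disorders, as applied to panic patients, includes the ADHD, antisocial and borderline diagnoses named for MDD.
3. Give the prior-functioning criterion a panic equivalent with its own reference period, or acknowledge the difference as a limitation of Study 2.
4. Leave the episode-duration criterion in the MDD list.

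The cost is a short amendment. The MINI suicidality screen and the clinical interview are already listed in Section 4. Because that section lets the team select among its measures, the amendment should commit to using both for panic candidates. A few panic candidates would fail screening, which matters a little in a group planned at 30 including 5 dropouts (25 completing).

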#### Control Groups:

- Panic Disorder patients: history of MDD or other relevant psychiatric or neurological disorders
- Healthy volunteers: history of axis-I disorder in family; history of psychiatric disorders or psychotropic medications

## 6. Protocol Consent Process and Documents

Each participant will receive an oral and written explanation of the purposes, procedures, and risks of this study in language appropriate for the individual's level of understanding. Written consent will be obtained after explaining the goals, procedures, risks (and discomforts), benefits, and nature of the studies to patients and control groups. Only adult healthy volunteers and patients who are capable of understanding the fMRI neurofeedback study procedures will be allowed to sign the consent forms.

## 7. Withdrawal of Subjects and Risk Management

A subject can decide to withdraw from the trial at any time and this will be made clear to the participants in the information sheets and consent forms. In this case, the subject must contact the Investigator and state that he/she is leaving the trial. The reason for withdrawal does not need to be stated; however the subject should feel free to do so.

The Investigator has to withdraw a subject from the study in the case of occurrence of a significant adverse event or any other condition, which in the opinion of the Investigator does not justify a safe continuation of the study. In the case of withdrawal, the subject's GP will be notified. Patients who experience adverse events will be offered advice by the consultant psychiatrist and Chief Investigator.

## 8. Evaluation of Benefits and Risks

## 8.1. Evaluation of benefits

There is a slight possibility that an individual participant might benefit from the earlier detection of occult neuropathology previously unrecognised when participating in the MRI arm of the study (e.g. tumors, strokes, arteriovenous malformations, etc.). There are no documented benefits to subjects participating at this point. However, this study aims at investigating the potential benefits of fMRI neurofeedback on self-blaming emotional bias in remitted depression. Even if such benefits will not be shown, the results of this study may be used to improve our design of tests that are sensitive to brain dysfunction, provide better outcome measures in clinical trials, and teach us about the neural and cognitive mechanisms of neuropsychiatric disorders which aid in the diagnosis and treatment of these disorders.

#### 8.2. Evaluation of risks

Risks from psychiatric assessments are minimal or non-existent. Some participants may find the interviews and tests tiring. To reduce this burden we have kept the number of clinical assessments to a minimum by using only relevant, widely used and validated assessment. MRI is safe when used on participants that are appropriately screened for the procedure (Shellock & Bierman, 1989). It is deemed that the risks to the participants in performing the neuropsychological, fMRI neurofeedback assessments in this protocol are minimal. Neurofeedback is reported to be a safe treatment, with only occasional reports of the occurrence of a possible side effect such as fatigue, headache, anxiety and difficulty falling asleep.

## 9. Assessment of Safety

#### 9.1. Procedures for recording and reporting adverse events

An adverse event (AE) is any untoward medical occurrence in a patient or healthy volunteer, which does not necessarily have a causal relationship with the study procedures (i.e., neuropsychological, neuroimaging assessments, or neurofeedback training). The period of recording of AEs will last from the time that the subject signs the informed consent form to the last trial day according to the clinical trial protocol.

#### 9.1.1. Adverse event recording

Each AE occurring to a subject either spontaneously revealed by the subject or observed by the Investigator, whether believed by the Investigator to be related or unrelated to assessment, will be recorded in the subject's source data.

The following aspects of AEs will be documented by the Investigator and the present medical support in the source data: each single symptom, if required possible diagnosis or syndrome, date and time of onset and end of AE, causal relationship with investigation (definite / probable / possible / unlikely / not related), outcome (resolved / resolving / not resolved / resolved with sequelae / fatal / unknown), treatment of event, if applicable (e.g. any medication as well as any other medical measures), actions taken regarding assessment.

#### 9.1.2. Adverse event reporting

The Investigator will report to the Chief Investigator all AEs, which occur during the trial, regardless of their relationship to the assessments by documentation in the case report form. In cases of medical emergencies the research team will adhere to the guidelines of the institute. In the case of patients and healthy controls, their GPs will be notified in writing of any significant adverse events.

#### 9.2. Termination criteria for participation

At each visit, patients will receive standard depression scales to assess changes in mood. The researcher will alert the study psychiatrist if the BDI-II suicidality item is rated above 0 and the subsequent MINI suicidality module results in a score indicating more than low risk. The psychiatrist will then offer a consultation and decide with the patient whether to continue with the study.

If the patient shows an increase of more than 10 points on the BDI-II during the course of the study, the patient will terminate the study and a consultation with the study psychiatrist will be offered. The GP will be informed.

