## 2.1.7. Outcome measures

Primary outcome measure:

 Reduction of depressive symptoms between Visit 1 and 5 as assessed by the Beck Depressive Inventory (BDI-II). (Reduction of depressive symptoms between Visit 1 and the last treatment session as assessed by the Beck Depressive Inventory (BDI-II) for those who do not complete the study.)

Secondary outcome measures:

- 2) Reduction of depressive symptoms between Visit 1 and 5 as assessed by the Montgomery–Asberg Depression Rating Scale (MADRS) by a rater who is blinded to the treatment arm.
- 3) Reduction of self-rated depressive symptoms between Visit 1 and 5 as assessed by the Quick Inventory of Depressive Symptomatology (QIDS-SR 16).
- 4) Clinical Global Impression scale change between Visit 1 and 5 by a rater who is blinded to the treatment arm.
- 5) Withdrawal rates and adverse events after first treatment session.
- 6) Decrease in post vs. pre-training right ATL-SSCR correlation on fMRI (in neurofeedback arm).
- 7) Reductions in implicit self-blaming bias (self-contempt bias BIAT) between Visit 1 and 5.
- 8) Increase in Rosenberg Self Esteem Scale score between Visit 1 and Visit 5.

- 9) Positive Affect score increase and Negative Affect score decrease (PANAS scale) between Visit 1 and Visit 5.
- 10) Profile of Mood States (POMS) depression score change between Visit 1 and 5.
- 11) Self-blame ratings obtained prior to the first and after the last treatment session.
- 12) Reductions in agency-incongruent self-blame on short version of the value-related moral sentiment task between Visit 1 and 5.
- 13) Dysfunctional Attitudes Scale (prior & post mood induction if time permits) between Visit 1 and 5.
- 14) Self- & observer rated clinical global impression on Visit 5 for change since Visit 1.

We may have to drop some of the secondary outcome measures, depending on time constraints.

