#### 2.1.8. Statistical power

Sample sizes (n=24 in each group, plus an estimated 12 lost to follow-up) were calculated (G\*POWER) to achieve 95% power at p=.05, 2-sided (t-test), based on a conservative estimate of an effect size (d=1.06) lower than that reported in a previous neurofeedback study of MDD.

Linden et al. (2012) reported a Cohen's d=1.5, with the neurofeedback group displaying a significant decrease (4.13  $\pm$  2.75 from a mean of 14.38 to 10.25 on the Hamilton-17 Depression Rating Scale).

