## 4. Diagnostic, Behavioural & Neuropsychological measures

From the following study measures we will select tests and measures which can be feasibly run within the stated time limits. We will therefore test the feasibility in a small group of patients to get a realistic time estimate and insure that patients and healthy controls are not overloaded with testing. All groups will have a baseline assessment of depressive symptoms (BDI-II, MADRS and QID-SR16) and experimental cognitive and emotional tests initially and as part of the post-trial assessment at Visit 5 (see outcome measures). Self-report scales (BDI-II and PANAS) will be carried out after each treatment session.

Clinical evaluation:

- Phone screening for exclusion and inclusion criteria of 15 to 20 minutes, major medical illnesses, substance abuse, axis-I disorders, pregnancy and MRI exclusion criteria, history of psychiatric and neurological treatments
- Non-structured clinical interview (all except healthy volunteers)
- Medical history including GP records if necessary (all)
- Day of menstrual cycle in women to use this as a covariate in the imaging analysis (in the high estrogen phase of the cycle brain activity is largely enhanced which adds variability to the data if not controlled for)
- Age at onset, episode duration, total illness duration
- MDD course: number of episodes, chronic, phasic, medication
- Beck Depression Inventory II (BDI-II; Beck & Brown, 1996)
- Montgomery-Asberg Depression Rating Scale (MADRS; Montgomery & Asberg, 1979)
- Global Social Functioning (GAF) Score (First et al., 2002)

- Psychiatric Family History Screen (Andreasen et al., 1977)
- AMDP Psychopathology Interview questions of depression items (translated from German; Faehndrich & Stieglitz, 1997; 2007)
- Mini International Neuropsychiatric Interview (MINI) suicidality Screen (Sheehan et al., 1998)
- Structured Clinical Diagnostic Interview (SCID)-I. Research Edition (First et al., 2002)
- Life Events Questionnaire (32 items). The scale aims to look at negative and positive life events, those occurring in the past and whether the respondent thinks they have a continuing influence and indicate whether the event was considered 'good', 'neutral' or 'bad'. Adapted from the List of Life Threatening Experiences (LTE; Brugha et al, 1985)
- Clinical Global Impression Scale (Busner & Targum, 2007)
- [LIFE] Longitudinal Interval Follow-up Interview (Keller et al., 1987)

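### The BDI-II stop rule ends study participation and not only treatment, so patients who cross it at Visits 2-4 have no planned blinded MADRS or CGI after baseline

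*Protocol*

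**What the plan says.** Protocol section 9.2 sets the rule: after an "increase of more than 10 points on the BDI-II during the course of the study, the patient will terminate the study". A consultation with the study psychiatrist is offered and the GP is told. Nothing else follows the stop. The suicidality rule just before it leaves continuation to the psychiatrist and patient; the BDI-II rule has no such discretion.

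Section 2.1.7 defines MADRS, QIDS-SR and CGI as changes from Visit 1 to Visit 5, for example "Clinical Global Impression scale change between Visit 1 and 5 by a rater who is blinded to the treatment arm". Its only provision for non-completers concerns the primary outcome, which is then taken "between Visit 1 and the last treatment session as assessed by the Beck Depressive Inventory (BDI-II) for those who do not complete the study".

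Section 4 schedules "depressive symptoms (BDI-II, MADRS and QID-SR16) and experimental cognitive and emotional tests initially and as part of the post-trial assessment at Visit 5". For the treatment visits it says "Self-report scales (BDI-II and PANAS) will be carried out after each treatment session". The flowchart in section 2.1.6 agrees: clinical assessment at Visits 1 and 5, and only an unspecified mood assessment at Visits 2-4. Section 9.2 is looser: "At each visit, patients will receive standard depression scales to assess changes in mood".

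Section 2.1.9 says that partial outcome data from patients lost to follow-up will enter the analyses. It provides for no collection after a stop.

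**The concern.** The trial is single-blind and its primary outcome is self-rated. Section 2.1.9 concedes that blinding is only partial and relies on blinded assessors for the observer-rated outcomes. MADRS and CGI are therefore the main check on the BDI-II result. The stop rule removes that check in patients selected because their BDI-II rose sharply, so the loss depends on outcome.

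If the arm that does worse is stopped more often, comparing only patients with a Visit 5 rating understates the difference on the blinded scales. A model that uses the recorded BDI-II can correct most of this, but it predicts ratings for patients who worsened from patients who did not. An analysis plan can choose such a model; it cannot supply a rating that was never taken. Whether Visit 5 takes place is a matter of data collection, which the protocol fixes.

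**Working it through.** **What is recorded for a patient stopped at Visits 2-4**

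| Measure | Planned times | After a stop at Visits 2-4 |
|---|---|---|
| BDI-II | Visit 1, after each treatment session, Visit 5 | Last-session value (2.1.7) |
| MADRS, blinded | Visits 1 and 5 | None planned |
| CGI, blinded | Visits 1 and 5 | None planned |
| QIDS-SR | Visits 1 and 5; treatment visits unclear (9.2) | Probably none |
| Withdrawals, adverse events | After the first treatment session | Recorded |

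**The protocol's own sample size.** Inputs from section 2.1.8: d=1.06, two-sided 5% t-test, 95% power. The noncentral t calculation gives 24.1 per arm, and power of 0.949 at 24 per arm. Adding 20% loss gives 48/0.8 = 60. The stated figures reproduce.

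**Size of the effect.** The protocol gives no standard deviation (SD) or correlation for BDI-II, so the following inputs are assumptions:
- Mean improvement of 8 points in one arm and 2 in the other, linear from Visit 1 to Visit 5: contrast -6.0.
- To match d=1.06, the SD of change must be 6/1.06 = 5.66.
- With equal correlation r between visits, SD of change = SD × √(2(1−r)). SD 9 with r=0.8 gives 9 × √0.40 = 5.69. SD 7 with r=0.67 gives 7 × √0.66 = 5.69. Both mean d of about 1.05.
- Normal scores, with the rule (more than 10 points above Visit 1) applied at Visits 2, 3 and 4.
- The change on the blinded scale has the same mean and SD as the BDI-II change and correlates 0.6 to 0.8 with it.
- 400,000 simulated patients per arm.

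| Setting | Stopped, by arm | Of 60 patients | Completers-only blinded contrast (true -6.0) |
|---|---|---|---|
| Equal correlation, SD of change 5.69 | 2.5% vs 6.7% | 30 × (0.025+0.067) = 2.8 | -5.77 to -5.86 |
| AR(1) correlation, SD of change 5.66 | 0.1% vs 1.2-1.3% | about 0.4 | -5.87 to -5.94 |

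Shrinkage with equal correlation runs from (6.00−5.86)/6.00 = 2% to (6.00−5.77)/6.00 = 4%. With AR(1) it is 1-2%.

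**Against sampling error.** With 24 per arm the standard error of the contrast is 5.69 × √(2/24) = 1.64. The shift of 0.14 to 0.23 points is 0.09 to 0.14 standard errors.

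**Primary outcome.** With the last-session fallback, the BDI-II contrast is about -6.24 with equal correlation and about -6.0 with AR(1), against -6.0.

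**Equal arms.** If both arms improve by 8 points (SD 9, r=0.8), about 1.5 of 60 are stopped and no contrast of any size appears. Data are lost, but there is no bias.

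**With modelling.** Predicting the missing rating within arm from its baseline value and the observed BDI-II returned a contrast between -5.94 and -6.03 in every 6-point setting tried, including SDs of 7 to 10.

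**The case against.** The strongest reply is that little turns on this. At the planned effect the rule stops a handful of patients at most, against 12 losses planned for all causes, and moves a secondary contrast by about a tenth of a standard error. The bias also presupposes a completers-only analysis, which the protocol does not choose: section 2.1.9 brings partial data into the analyses, and modelling on the recorded BDI-II removes most of the bias. All of this stands, and it limits the weight of the point. It does not restore the blinded ratings.

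Four stronger readings are tempting, and the document does not support them:
- *That every patient who worsens is lost.* Only a rise of more than 10 points at Visits 2-4 matters. Smaller rises do not trigger the rule, and a rise first seen at Visit 5 occurs where the blinded scales are already scheduled.
- *That QIDS-SR is certainly lost.* Section 9.2 speaks of depression scales, in the plural, at each visit. Section 4 names BDI-II and PANAS after sessions without saying that there are no others, and PANAS measures affect. The gap is firm only for MADRS and CGI.
- *That the loss could be large.* About 14 of 60 stopped (SD 10, equal correlation 0.5) or shrinkage near 15% (SD 10, AR(1) 0.8) requires an SD of change of about 10 to 11, hence d of about 0.55 to 0.60. That is well below the value given as "based on a conservative estimate of an effect size (d=1.06) lower than that reported in a previous neurofeedback study of MDD".
- *That deterioration is hidden or the primary result undermined.* The triggering BDI-II is recorded, the fallback uses it, and "Withdrawal rates and adverse events after first treatment session" is itself an outcome.

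It can also be said that Visit 5, timed from the last treatment visit, might still take place after an early stop. The wording of the rule and the last-session fallback both point the other way. Finally, scores taken after a stop may partly reflect care begun since. That is a real limit on the remedy, and a reason to record such care.

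**Conclusion.** The point holds as a modest one, worth considering. As written, the rule ends participation, and no section preserves the blinded MADRS or CGI for patients who cross it at Visits 2-4; QIDS-SR is uncertain.

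At d=1.06 with a 6-point contrast, about 0.4 to 3 of 60 patients are affected and a completers-only blinded contrast shrinks by about 1-4%, small against a standard error of about 1.6 points. These figures rest on an assumed BDI-II spread, assumed correlations, normal scores and linear change, none of which the protocol gives. The primary contrast moves by roughly 0.2 points or less in the same settings. The case for acting rests on how cheaply blinded ratings can be kept in the patients most informative about harm. It does not rest on any expectation that a conclusion of this pilot would change.

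**What to change.** Keep the stop, the consultation and the GP notice. Amend section 9.2 to say that the rule ends the intervention only. Patients who agree then attend a shortened Visit 5 in its scheduled window (7-13 days after the last treatment visit), limited to BDI-II, QIDS-SR and blinded MADRS and CGI.

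In section 2.1.7, use Visit 5 scores where they are obtained and keep the last-session BDI-II fallback only when Visit 5 is refused. Record any care started after the stop. State in section 4 which depression scales are given at treatment visits, which would settle the QIDS-SR question.

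The cost is protocol and consent wording, and one already planned visit for a few unwell patients who consent. Section 3 allows up to 3 hours of testing per day for patients, hence the shortened form. Some scores will partly reflect care received after the stop.
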